8.4.3 REPORTING UNANTICIPATED PROBLEMS TO PARTICIPANTS

N/A.

9 STATISTICAL CONSIDERATIONS

9.1 STATISTICAL HYPOTHESES

This randomized trial will compare the effects of a Mediterranean-style (Med-style) dietary pattern intervention to an augmented usual care control group in primary care clinics. The objectives of this trial are:

Primary Aim (efficacy): Weight loss at 24 months. Hypothesis: Mean weight loss in the intervention group will exceed that in augmented usual care by $\geq 4\%$ of initial body weight (e.g., $\geq 5\%$ intervention, $\sim 1\%$ control).

Secondary weight outcomes: Assess difference between study groups in proportion losing $\geq 5\%$ body weight and differences in mean weight loss and proportion losing $\geq 5\%$ across 3 pre-specified subgroups: 1) with vs. without diabetes; 2) females vs. males; and 3) Whites vs. African Americans.

Secondary Aim 1—Physiologic and Lifestyle Outcomes: Assess change in blood pressure, A1c, markers of inflammation, skin carotenoids, and self-reported dietary patterns by study group.

Secondary Aim 2—Process and Psychosocial Factors: Assess process variables (attendance, fidelity, and acceptability of the Med-style dietary intervention), and key behavioral and psychosocial variables, including self-regulation/monitoring skills, self-efficacy, motivation, and quality of life.

Secondary Aim 3--Economic Outcomes: Assess implementation cost, and incremental cost-effectiveness of the intervention relative to control in terms of cost per percentage reduction in weight (i.e., kg lost) and cost per quality adjusted life years (QALYs) gained.

9.2 SAMPLE SIZE DETERMINATION

Note: the text below was written for an anticipated sample size of 350. We now plan to enroll 360 participants.

For our primary outcome, percent change in weight at 24 months, we have calculated sample size based on a two-sided test of

significance with $\alpha=0.05$

and the standard deviation (SD) of percent change in weight of 7.3% as observed in the Heart Health Lenoir Project^{74, 75}. Table 4 illustrates sample size calculations (allowing for 20% attrition) for various differences in mean changes between study groups based on a

1:1 randomization allocation ratio. This table also provides power calculations to detect differences in weight change compared to control separately for pre-specified subgroups (those with vs. without diabetes, female vs. male, and white vs. African American assuming no sub-group is less than 40% of the overall sample). We expect the intervention to reduce weight by at least 5% and that average weight loss in the intervention group will exceed that in augmented usual care by at least 4% (we estimate weight loss in usual care of $\leq 1\%$). Our plan to enroll 350 participants provides excellent power for our primary outcome ($>99\%$) and reasonable power (82%) within each of our pre-specified sub-groups. For a difference between groups as small as 3%, we still have robust power for our primary outcome.

Although we do not anticipate major differences in weight loss between those in our pre-specified subgroups, we will test the potential for large

differential effects between subgroups using interaction terms. However, under the assumptions described above, our power to detect realistic difference in effects of 2-3% between these subgroups will be limited (about 20-40%). Also, for a difference in proportions of those losing $\geq 5\%$ body weight as small as 15% (e.g., 15% control vs. 30% intervention), allowing for attrition, the proposed sample size provides 85% power. For several secondary outcomes, we present in Table 5 minimally detectable differences corresponding to effect size of 0.33 for the sample size of 360 with 20% attrition, 80% power, and $\alpha =0.05$

Table 4. Power Estimates for % Change in Weight at 24 Month Follow-up			
Assumed Mean % Change Difference Between Groups	Total Sample Size	Overall Power to Detect Difference	Minimum Power within Each Subpopulation (Diabetes status, sex, and race) to Detect Specified Difference
3	300	89%	51%
	350	93%	58%
	400	96%	64%
4	300	98.8%	76%
	350	99.5%	82%
	400	99.8%	87%

Table 5. Secondary Outcomes (at 24 month)		
Secondary Outcomes	SD of change	Difference in mean changes
Systolic BP	23.1	7.6
Diastolic BP	11.1	3.6
A1c (%)	0.4	0.1
CRP	0.9	0.3
Dietary pattern assessed by	0.3	0.1

9.3 POPULATIONS FOR ANALYSES

Intention-to-Treat (ITT) Analysis Population (i.e., all randomized participants)

9.4 STATISTICAL ANALYSES

9.4.1 GENERAL APPROACH

This is covered in Section 9.4.2.

Update 6/8/25: Our analysis plan as submitted with this protocol is below. Before we assessed study outcomes, we prepared a more detailed statistical analysis plan. This is included in 9.4.3 below:

9.4.2 ANALYSIS OF THE PRIMARY ENDPOINT(S)

The primary analysis will be conducted using the ITT Population and will be repeated secondarily using the Per Protocol Population.

Percent change in body weight = (Follow-up weight – baseline weight)/baseline weight x 100. We will compare the longitudinal mean % change in body weight between groups using analysis of covariance (ANCOVA), conducted using a linear mixed model. A mixed model will allow for the inclusion of all observed follow-up data for all participants. The model will include fixed effects for group, follow-up visit (4, 12, or 24 months), group-by-visit interactions, site, baseline weight, race/ethnicity, sex, and diabetes status. To account for within-participant correlation, the model will allow for correlated error terms using an unstructured covariance matrix. For the primary comparison, we will use an appropriately specified linear contrast of the model parameters to test for a treatment effect at 24-months at the 5% significance level. Secondarily, we will compare the groups at other time points and will estimate effect sizes along with 95% confidence intervals for each comparison. Secondarily, we will expand the model by including appropriate interaction terms, one at a time, to examine the potential heterogeneity of intervention effect in sub-groups, including diagnosis (diabetes vs. no diabetes), race/ethnicity, sex, and by degree of baseline obesity (BMI > 40 vs. less). Interaction terms will be tested at the 5% significance level.

We will use a longitudinal mixed effects logistic regression model to compare the groups for proportions losing > 5% body weight at each follow-up visit; estimates of odds ratios and 95% confidence intervals will be provided. This model will control for the same covariates specified for the primary model.

Missing Data

We will make every effort to prevent missing data and to minimize attrition, however some dropout is expected. We will record reasons for dropouts to formulate realistic assumptions about observations that are missing, and compare respondents and non-respondents for differences on values of non-missing variables. We will conduct a series of sensitivity analyses using similar models to evaluate the robustness of conclusions drawn from the primary model to departures from MAR assumption by comparing the magnitude of the primary treatment contrast. Specifically, we will use 1) multiple imputation including auxiliary information about the missingness; 2) shared-parameter models for not missing at random analyses where one variable is the efficacy outcome and the second variable is time to dropout, linked by a set of latent variables that are assumed to influence both the outcome and the

time to dropout; (3) patterning-mixture model, with models for each pattern of missing ness (e.g., by study phase); and (4) worst-case imputation, with baseline carried forward for intervention participants and best observation carried forward for control participants.

9.4.3 ANALYSIS OF THE SECONDARY ENDPOINT(S)

Analysis of Secondary Objectives (1-2)

The ITT Population will be used in the primary analysis of all secondary outcomes. Similar ANCOVA methods to those described above will be used to compare groups on each of the secondary outcomes; for any outcome measured at baseline, the corresponding ANCOVA will control for baseline value in addition to the covariates noted above. Blood pressure will be averaged over three repeated measurements at each visit. Because they are of secondary interest, tests on secondary outcomes will each be conducted at the 5% significance level with no adjustments for multiple comparisons. All estimates of effect size will be accompanied by 95% confidence intervals. Data from all secondary outcomes will be presented regardless of extent of “significance”. Descriptive summaries of process data (attendance at intervention contacts, fidelity to intervention delivery, and acceptability of the Med-style dietary pattern) will be provided for participants randomized to Group 1 in the ITT Population. No inferential statistics (p-values or confidence intervals) will be presented.

Analysis of Secondary Objective 3 (Economic Analysis)

We plan to conduct both a budgetary impact assessment and a cost-effectiveness analysis. The budgetary impact assessment will quantify the total and per participant costs of intervention delivery from the health system perspective using an Activity Based Costing (ABC) approach and cost tracking forms that the health economist ([name])¹⁵⁸⁻¹⁶⁰ has developed and refined in past behavioral trials. Using this approach, all relevant labor, materials and supplies, contracted services, and other relevant costs required to deliver the interventions will be captured by key activities. This information will allow policy makers to identify the total and per capita fixed and variable costs of the intervention and to forecast required budgets, should the intervention expand beyond the trial phase. The non-sunk cost estimates will also feed into the cost-effectiveness analysis.

The incremental cost-effectiveness analysis will follow the approach [name] has employed in prior studies, including a manuscript on the cost-effectiveness of commercial weight loss programs.^{161, 162} We will compute the incremental cost per kilogram of weight loss relative to control, and using the approach presented in [name] and Kruger,¹⁶¹ the incremental cost per quality adjusted life year (QALY) gained. The numerator for this analysis will be the incremental program delivery costs of the intervention relative to control, minus any cost offsets based on differences in health services and medication use across arms. The denominator will be the incremental QALYs based on average differences in EQ5D¹⁴⁶ scores across arms collected at each assessment point. These scores can be used to quantify net QALY differences during the intervention period. In the base case, we will assume that QALY benefits decay linearly to 0 by the end of the second year post cessation of the study. All out-year cost and QALY estimates will be discounted at 3.5% per annum.

To test for the sensitivity of our incremental cost-effectiveness ratio (ICER) estimates to changes in key inputs, we will conduct one-way sensitivity analyses by (1) doubling or halving all key model inputs; and

(2) varying the duration of benefit decay post program cessation from 2 years in both base cases to 0, 1, and 3 years. We will also conduct probabilistic sensitivity analyses to assess the effect of uncertainty regarding all input parameters using appropriate distributions for all cost and QALY values. Using the results, we will produce cost-effectiveness acceptability curves that graphically present the probability that the intervention is cost-effective for a range of willingness to pay metrics that a decision maker may consider. Based on the results, we will discuss the extent to which the intervention is likely to be both affordable and cost-effective

6/9/25: Note: a separate Statistical Analysis Plan was prepared for this study. This will be submitted to clinicaltrials.gov and journals as a separate document.

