8 STUDY ASSESSMENTS AND PROCEDURES

8.1 ENDPOINT AND OTHER NON-SAFETY ASSESSMENTS

8.1.1: Screening, eligibility assessment, and consent

- Outlined in detail in Section 5.5, Strategies for Recruitment and Retention.

8.1.2: Overview of study measures

Study data will be collected at baseline, 4, 12, and 24 months. Process data for the intervention group (Med-South Weight Loss Program) will be collected as part of the intervention via the web-based platform and via REDCap questionnaires completed by counselors immediately after counseling sessions. Process data for the enhanced usual care group will be assessed via a Data Use Agreement with WW™ and by questionnaire at follow-up visits. *As recommended by NIH, our measures include ADOP^T¹³⁷⁻¹³⁹ core constructs (in blue) and specific instruments (in blue underlined) as noted in the Table.*

Primary and Secondary Aims 1 and 2:

Table 3: Outcomes/ Measures	Collection Time (min)	Data collected times (months)				Comment
		0	4	12	24	
Weight (primary outcome) , by electronic scale as the average of two measures, and height (baseline only). SECA 874 dr scales will be used and assessed monthly for accuracy with standardized weights..	5	x	x	x	x	At study outset, seven standardized 50 lb. weights certified for accuracy by NC state standards lab.*
Secondary Outcomes						
Objective measures						
--Blood pressure by noninvasive automated monitor (Omron HEM-907XL, Vernon Hills, IL) with a first measure after seated for 5 minutes and 2 repeat measures at 1-minute intervals	10	x	x	x	x	
--Blood work: performed by LabCorp 
Fasting lipid panel: total cholesterol, triglycerides, HDL, and calculated LDL and VLDL. If participants are unable to fast a non-fasting sample is collected with non-fasting stat notedA1cOther chemistry: glucose, ALT, creatinine (if not previously checked in prior 2 years and only at baseline), and CRP	10	x	x	x	x	Creatinine collected at baseline for those without measure in preceding 2 years.

--blood work: preformed in lab of [name]. Serum and plasm specimens are frozen to – 80 C. immediately after collection and processing. • interleukin (IL)-6, tumor necrosis factor (TNF)-alpha, and C-reactive protein (C-RP)						
--skin carotenoids, Reflection Spectroscopy Device ("Veggie Meter"™) ¹⁴⁰⁻¹⁴²	5	x	x	x	x	

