Questionnaires:						These data collected before the actual visit, on-line via REDCap or by phone. Window before baseline visit is 4 weeks. Window before follow-up and after follow-up visits is 2 weeks.
--Demographics and medical history (baseline only)	15	x				
--Diet assessment: diet quality, ¹⁴³ adapted PREDIMED checklist ^{19, 96}	10	x	x	x	x	
--Detailed assessment of diet quality: Willett Food Frequency Questionnaire ¹⁴⁴	20-30	x	x	x	x	
--Physical activity and sedentary behaviors: GPAQ for physical activity and sedentary behavior , ¹⁴⁵ participant report of monitored steps	5	x	x	x	x	
--Quality of life (EQ5D ¹⁴⁶)	5	x	x	x	x	
--Food insecurity ¹⁴⁷	2	x	x	x	x	
Diet Self-Efficacy Scale ¹⁴⁸	3	x	x	x	x	
Weight Loss Self-efficacy Short-Form (WEL-SF1) ^{149, 150}	3	x	x	x	x	
Early Self-Weighing Questionnaire ¹⁵¹	1	x	x	x	x	
Self-Regulation: Dietary Self-Regulation (TSRQ) ¹⁵²	3	x	x	x	x	
Three-Factor Eating Questionnaire ¹⁵³	3	x	x	x	x	
Mindful Eating Questionnaire ¹⁵⁴ **	5	x	x	x	x	

Perceived Stress Scale ¹⁵⁵	3	x	x	x	x	
PHQ-8 ¹⁵⁶	3	x	x	x	x	
--Medications for high BP, high blood lipids, diabetes, and weight loss (self-report with EHR review)	5	x	x	x	x	
--Adverse outcomes, CVD events, ER visits, and hospitalizations (follow-up only)	5		x	x	x	
--Acceptability (follow-up only)	5-10		x	x	x	
Diet and PA goals and success achieving goals (collected by web-based intervention platform and counselor)	NA					Collected after each counseling session in intervention group.
Exploratory Outcome						
Stool microbiome (participants may elect not to complete this measure)	NA	x	x	x	x	First sample will be collected in the 2 week period immediately after randomization. (These are the only baseline data collected after randomization.) The follow-up samples will be collected w/n a 2 week window of follow-up visit date.
Other						
--EHR to assess/confirm adverse health outcomes	NA		x	x	x	To confirm information collected by questionnaire at these visit time points

* <http://www.ncagr.gov/standard/Labs/>

**Added to baseline on 12/22/20. No follow-up data had been collected at this point in the study.

Note: table last updated 3/1/21

Additional Study measures—economic outcomes

The budgetary impact assessment and numerator for the cost effectiveness analysis will be based on Activity Based Costing Questionnaires previously developed and applied by [name] in similar studies^{99, 157} along with participants' health care claims data that will be used to compare resource

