### 9.4.4

### Secondary Analyses

The ITT Population will be used in the primary analyses of all secondary outcomes. Similar ANCOVA methods to those described in the primary outcome analyses will be used to compare groups on each of the secondary outcomes. For any outcome measured at baseline, the corresponding ANCOVA will control for baseline value in addition to the covariates noted above. Because they are of secondary interest, tests on secondary outcomes will each be conducted at the two-sided 5% significance level without adjustments for multiple comparisons. All estimates of effect size will be accompanied by 95% confidence intervals. Data from all secondary outcomes will be presented regardless of extent of "significance".

Descriptive summaries of process data (attendance at intervention contacts, fidelity to intervention delivery, and acceptability of the Med-South dietary pattern) will be provided for participants randomized to the Med-South dietary pattern intervention group in the ITT Population. No inferential statistics (p-values or confidence intervals) will be presented.

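### The QALY denominator is defined from average EQ-5D differences between arms, with no stated adjustment for baseline EQ-5D

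*Protocol*

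**What the plan says.** The economic part of Protocol 9.4.3 (Secondary Objective 3) defines the QALY side of the ratio: "The denominator will be the incremental QALYs based on average differences in EQ5D" "scores across arms collected at each assessment point". It adds: "These scores can be used to quantify net QALY differences during the intervention period". No formula turns scores into QALYs, and no covariate is named. Beyond the trial, "we will assume that QALY benefits decay linearly to 0 by the end of the second year post cessation of the study", and "All out-year cost and QALY estimates will be discounted at 3.5% per annum".

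The assessment points include baseline. Protocol 8.1.2 says "Study data will be collected at baseline, 4, 12, and 24 months", and the Table 3 row "Quality of life (EQ5D" is marked at all four times.

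The baseline rule stands elsewhere. Protocol 9.4.3 gives it in the part on Secondary Objectives 1 and 2. SAP 9.4.4 repeats it for secondary outcomes generally: "For any outcome measured at baseline, the corresponding ANCOVA will control for baseline value". Quality of life belongs to Secondary Aim 2, so EQ-5D as an outcome in its own right is covered.

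The SAP has no economic methods section. SAP 7.3 makes the economic analysis conditional on a weight difference above 2.5% and refers to Objective D, although economics is item e in the SAP's own list of objectives.

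**The concern.** A between-arm difference in EQ-5D at entry cannot be a treatment effect. If QALYs are built from differences in average scores at every visit, that gap is counted in two ways: through the weight given to the baseline visit, and through the correlation of later scores with baseline. The decay assumption then carries the 24-month difference forward for two more years.

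The quality-of-life analysis would remove this gap by ANCOVA, but the economic section does not say that its result is used. The same EQ-5D data could therefore yield an adjusted effect in one table and an unadjusted QALY difference in another. The planned sensitivity analyses (doubling or halving inputs, varying the decay period, probabilistic analysis) describe uncertainty around the estimate. None removes a baseline imbalance.

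**Working it through.** **Plan's own figure.** The documents give no expected QALY gain, EQ-5D SD or correlation. The nearest stated figure is the detectable effect of 0.33 for secondary outcomes (Protocol 9.2: 360 participants, 20% attrition, 80% power, alpha 0.05). With 360 × 0.8 / 2 = 144 per arm, (1.960 + 0.842) × √(2/144) = 0.330. It reproduces.

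**Inputs.** From the documents: 180 per arm (360, 1:1); visits at 0, 4, 12 and 24 months; two-year linear decay. Assumed: EQ-5D SD 0.10-0.20; equal correlation ρ between any two visits, 0.6-0.8, with 0.4 as a low case; trapezoid area under the curve.

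**Visit weights (years).** The trapezoid rule gives w0 = 0.167, w4 = 0.500, w12 = 0.833, w24 = 0.500, summing to 2. The decay is a triangle of base 2 years, so it adds T = 1.0 to the weight on the 24-month difference, undiscounted.

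**Chance baseline gap.** SE = SD × √(2/180), which is 0.0105 at SD 0.10 and 0.0211 at SD 0.20. Multiplying by 1.96 gives 95% limits of 0.0207 and 0.0413.

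**Carry-over.** Given a baseline gap b and no treatment effect, the expected unadjusted QALY difference is k × b, where k = w0 + ρ(w4 + w12 + w24 + T), and T = 0 within the trial.

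| ρ | k, 24 months | QALY at 95% gap, SD 0.10 to 0.20 | k, with decay | QALY at 95% gap, SD 0.10 to 0.20 |
|---|---|---|---|---|
| 0.4 | 0.167 + 0.4 × 1.833 = 0.900 | 0.019 to 0.037 | 1.300 | 0.027 to 0.054 |
| 0.6 | 0.167 + 0.6 × 1.833 = 1.267 | 0.026 to 0.052 | 1.867 | 0.039 to 0.077 |
| 0.8 | 0.167 + 0.8 × 1.833 = 1.633 | 0.034 to 0.067 | 2.433 | 0.050 to 0.10 |

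Discounting the decay period continuously at 3.5% from baseline lowers its weight from 1.0 to 0.912, which changes little.

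**Precision.** The unadjusted variance is (2 SD²/n) × [(1 − ρ)Σw² + ρ(Σw)²], with Σw² = 1.222 and (Σw)² = 4. Adjustment removes (2 SD²/n) × k². At SD 0.20 and 180 per arm, for the 24-month QALY difference:

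| ρ | bracket | k² | SE unadjusted | SE adjusted | reduction |
|---|---|---|---|---|---|
| 0.4 | 2.333 | 0.810 | 0.0322 | 0.0260 | 19% |
| 0.6 | 2.889 | 1.604 | 0.0358 | 0.0239 | 33% |
| 0.8 | 3.444 | 2.668 | 0.0391 | 0.0186 | 52% |

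The percentage reduction does not depend on the SD or on n. With 144 per arm, every gap and SE grows by √(180/144) = 1.12.

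**The case against.** The plan never says raw or unadjusted. Both planning documents require baseline adjustment of EQ-5D as a quality-of-life outcome, and the adjusted differences from that model are a natural source for the differences in the economic section. That section also defers to an approach in a cited study, which cannot be checked here. Randomisation protects the estimate on average, and the analysis may never be run.

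Most of this stands, and it limits what can be claimed. A reader might infer that the sponsor has chosen unadjusted means, that EQ-5D is the one outcome left out of the baseline rule, or that imbalance will decide the sign of the cost per QALY. The documents support none of these. Adjustment is neither stated nor ruled out. EQ-5D as an outcome falls within the rule, while stool microbiome, for example, has a baseline sample and no stated model. No expected QALY gain is given against which to judge a change of sign. Nor does a baseline gap pass through in full: its follow-up part is scaled by ρ.

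What the objection does not supply is a sentence connecting the adjusted EQ-5D differences to the QALYs. The baseline visit is among the assessment points, so the text as written leads to an unadjusted difference.

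**Conclusion.** The point holds as a gap in specification, with a better method available at almost no cost. It is not a demonstrated error in the estimate: the harm is bias conditional on whatever baseline imbalance occurred, together with avoidable loss of precision. The sizes above rest wholly on the assumed SD, equal correlations and trapezoid formula. The precision gain stays worthwhile at the low correlation of 0.4. The primary endpoint is not affected, and the matter is moot if the 2.5% condition is not met. Cost per QALY is nonetheless a named secondary aim. Because the economic analysis is triggered by the weight result, an unspecified QALY method would be settled after that result is known.

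**What to change.** Add an economic methods paragraph to the SAP, dated and agreed before EQ-5D by arm is examined for this purpose:

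- Compute each participant's area-under-the-curve QALY over 0, 4, 12 and 24 months, and state the rule for missing EQ-5D visits.
- Estimate the arm difference by regression on arm, baseline EQ-5D and the primary-model covariates.
- Base the decay extrapolation on a baseline-adjusted 24-month difference.
- Use the adjusted difference and its uncertainty in the cost-per-QALY ratio and acceptability curve, for example by bootstrapping costs and QALYs jointly.
- Correct the reference in SAP 7.3 so that it points to the economic objective.

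No new data are needed. The cost is a paragraph of text and one regression in place of a difference in means.
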